 - i. Tumors invading the GI-tract, active peptic ulcer disease, inflammatory bowel disease, diverticulitis, cholecystitis, symptomatic cholangitis or appendicitis, acute pancreatitis or acute obstruction of the pancreatic or biliary duct, or gastric outlet obstruction.
 - ii. Abdominal fistula, GI perforation, bowel obstruction, or intra-abdominal abscess within 6 months prior to randomization. Complete healing of an intra-abdominal abscess must be confirmed prior to randomization.
 - iii. Gastric or esophageal varices that are untreated or incompletely treated with bleeding or high risk for bleeding. Subjects treated with adequate endoscopic therapy

(according to institutional standards) without any episodes of recurrent GI bleeding requiring transfusion or hospitalization for at least 6 months before randomization are eligible.

- c. Clinically significant hematuria, hematemesis, or hemoptysis of > 0.5 teaspoon (2.5 ml) of red blood, or other history of significant bleeding (eg, pulmonary hemorrhage) within 3 months before randomization.
- d. Cavitating pulmonary lesion(s) or known endobronchial disease manifestation.
- e. Lesions invading major blood vessel, including, but not limited to: inferior vena cava, pulmonary artery, or aorta. Subjects with lesions invading the intrahepatic vasculature, including portal vein, hepatic vein, and hepatic artery, are eligible.
- f. Other clinically significant disorders such as:
 - i. Active or history of autoimmune disease or immune deficiency, including, but not limited to, myasthenia gravis, myositis, autoimmune hepatitis, systemic lupus erythematosus, rheumatoid arthritis, psoriatic arthritis, inflammatory bowel disease, antiphospholipid antibody syndrome, Wegener granulomatosis, Sjögren's syndrome, Guillain-Barré syndrome, or multiple sclerosis (see [Appendix D](#) for a more comprehensive list of autoimmune diseases and immune deficiencies). Subjects with the following conditions are eligible for the study:
 - A history of autoimmune-related hypothyroidism and on thyroid replacement hormone
 - Controlled Type 1 diabetes mellitus and on an insulin regimen
 - Asthma that requires intermittent use of bronchodilators
 - Eczema, psoriasis, lichen simplex chronicus, or vitiligo with dermatologic manifestations only provided all of following are true:
 - Rash covers < 10% of body surface area
 - Disease is well controlled at baseline and requires only low-potency topical corticosteroids
 - No occurrence of acute exacerbations of the underlying condition requiring psoralen plus ultraviolet A radiation, methotrexate, retinoids, biologic agents, oral calcineurin inhibitors, or high potency or oral corticosteroids within the previous 12 months
 - ii. Any condition requiring systemic treatment with either corticosteroids (> 10 mg daily prednisone equivalent) or other immunosuppressive medications within 14 days before randomization.
Note: Inhaled, intranasal, intra-articular, and topical corticosteroids and mineralocorticoids are permitted.
Transient use of systemic corticosteroids for allergic conditions such as contrast allergy is allowed.
 - iii. Active infection requiring systemic treatment, known history of infection with human immunodeficiency virus (HIV) or acquired immunodeficiency syndrome

(AIDS)-related illness, or a known positive test for tuberculosis due to tuberculosis infection. Subjects with active hepatitis B virus infection controlled with antiviral therapy are eligible (see Inclusion Criterion 3). Subjects with active, uncontrolled hepatitis C virus infection are eligible provided liver function meets eligibility criteria and are receiving management of the disease per local institutional practice (note: antiviral treatment for HCV is allowed with Sponsor approval). Subjects with history of COVID-19 must have recovered from the disease at least 30 days prior to randomization.

- iv. History of idiopathic pulmonary fibrosis, organizing pneumonia, drug-induced pneumonitis, idiopathic pneumonitis, or evidence of active pneumonitis on screening chest CT scan
- v. Serious non-healing wound/ulcer/bone fracture.
- vi. Malabsorption syndrome.
- vii. Symptoms of thyroid dysfunction with thyroid function test corroboration (*Note: asymptomatic subjects with an isolated abnormal free thyroxine [FT4] are eligible*)
- viii. Moderate to severe hepatic impairment (Child-Pugh B or C [[Appendix J](#)]).
- ix. Requirement for hemodialysis or peritoneal dialysis.
- x. History of solid organ transplant including liver transplant, or allogeneic stem cell transplant.

12. Major surgery (eg, GI surgery, removal or biopsy of brain metastasis) within 8 weeks before randomization. Minor surgeries within 10 days before randomization. Subjects must have complete wound healing from major surgery or minor surgery before randomization. Subjects with clinically relevant ongoing complications from prior surgery are not eligible.

13. Corrected QT interval calculated by the Fridericia formula ($QTcF > 480$ ms per electrocardiogram (ECG) within 14 days before randomization.

Note: If a single ECG shows a $QTcF$ with an absolute value > 480 ms, two additional ECGs at intervals of approximately 3 min must be performed within 30 min after the initial ECG, and the average of these three consecutive results for $QTcF$ will be used to determine eligibility

14. History of psychiatric illness likely to interfere with ability to comply with protocol requirements or give informed consent

15. Pregnant or breastfeeding females.

16. Inability to swallow tablets.

17. Previously identified allergy or hypersensitivity to components of the study treatment formulations or history of severe hypersensitivity to monoclonal antibodies. Subjects with rare hereditary problems of galactose intolerance, the Lapp lactase deficiency or glucose-galactose malabsorption are also excluded.

18. Any other active malignancy at time of randomization or diagnosis of another malignancy within 2 years before randomization that requires active treatment, except for superficial skin cancers, or localized, low grade tumors deemed cured and not treated with systemic therapy.

ESTIMATED LENGTH OF SUBJECT PARTICIPATION

It is estimated that subjects will receive study treatment for an average of approximately 6 months. Subjects will be followed until death, withdrawal of consent for non-interventional study assessments, or Sponsor decision to no longer collect survival data.

ESTIMATED STUDY DATES

It is estimated that approximately 25 months will be required to randomize 740 subjects at approximately 250 global sites for the global enrollment phase of the study. The number of events required for the final analyses of the primary PFS (257 events among the first 372 randomized subjects within the cabozantinib + atezolizumab combination and sorafenib arms) and primary OS (368 events among the 555 randomized subjects within the cabozantinib + atezolizumab combination and sorafenib arms) is expected to be observed around approximately 18 months and around 38 months, respectively, after the first subject is randomized.

After completion of the global enrollment phase, additional subjects (up to 148) may be enrolled in a Mainland China Extension Phase at sites in mainland China for evaluation in a China subpopulation. It is estimated that randomization of the subjects in mainland China during the global enrollment phase and Mainland China Extension Phase will require at least 21 months.

The true intervals required to meet the milestones above may be longer or shorter due to divergence from assumptions, including non-constant accrual rate due to the time required for all study sites to become active, or due to the impact of the global COVID-19 pandemic on subject enrollment and other aspects of study conduct.

INVESTIGATIONAL REGIMEN DOSE/ ROUTE/ DURATION

Subjects in the experimental arm will take oral study medication (40 mg of cabozantinib: 2 tablets containing 20 mg each of cabozantinib) once daily. Atezolizumab will be administered IV every 3 weeks at 1200 mg dose.

Dose reduction levels of cabozantinib will be allowed in the experimental arm (20 mg qd and 20 mg every other day [qod]). Dose reductions for atezolizumab will not be allowed and AEs will be managed by dose delays. Escalation of cabozantinib from 40 mg qd to 60 mg qd is allowed after Sponsor approval for subjects who are tolerating the 40 mg cabozantinib dose level well and have been treated on this dose level for at least 4 weeks. In general, subjects who develop clinically relevant adverse events (eg, Grade 3 or 4 AEs) are not allowed to dose escalate cabozantinib from 40 qd to 60 mg qd.

Subjects in the control arm will take sorafenib orally (2 tablets containing 200 mg each of sorafenib) twice daily. Dose interruptions and reductions will be allowed as per local prescribing information.

Subjects in the single-agent cabozantinib arm will take 60 mg of cabozantinib qd (1 tablet of 60 mg of cabozantinib). Two dose reduction levels of cabozantinib will be allowed in this arm

(40 mg daily and 20 mg daily). Subjects may be allowed to re-escalate following a dose reduction according to the guidance provided in [Section 6.6.1](#).

Subjects will continue study treatment as long as they continue to experience clinical benefit in the opinion of the Investigator (see [Section 5.8.6.3](#)) or until unacceptable toxicity, the need for alternative anticancer treatment, or other reasons for treatment discontinuation. Continuation of one component of the combination study in the experimental arm (cabozantinib and atezolizumab) while discontinuing the other will be allowed as per protocol defined guidelines.

SAFETY ASSESSMENTS

Safety will be assessed on a schedule based on the date of the first dose (W1D1) and every 3 weeks thereafter. Routine safety follow-up visits will be performed 30 (+14) days (FU-1) and approximately 100 (\pm 14) days (FU-2) after the date of the decision to permanently discontinue study treatment. Further details for follow-up and data collection requirements for AEs, SAEs, and AESIs are summarized in [Appendix K](#).

Routine safety evaluations will include physical examination, vital signs, performance status, 12-lead ECG, hematology, serum chemistries, coagulation tests, urine tests (including UPCR), serum pregnancy tests (in females of childbearing potential), and thyroid function tests. Adverse event seriousness, severity grade, relationship to study treatment, and relationship to immune effects (ie, irAEs) will be assessed by the Investigator. Severity grade will be defined by the National Cancer Institute (NCI) CTCAE v5.

An Independent Data Monitoring Committee (IDMC) will be established to monitor safety of the study on a regular basis. The IDMC will operate independently from the Sponsor and the clinical investigators.

EFFICACY ASSESSMENTS

Subjects will be monitored for radiographic response and progression per RECIST 1.1. For determining radiographic endpoints, radiographic assessments will be assessed by the BIRC and Investigator; radiographic assessment by the Investigator will be used for treatment decisions. Overall survival will be assessed at scheduled visits and every 12 weeks (\pm 14 days). Subjects will be followed until death, withdrawal of consent for non-interventional study assessments, or Sponsor decision to no longer collect these data.

TUMOR ASSESSMENTS

Study Eligibility by Imaging-Based Diagnosis: Clinical diagnosis of HCC by multiphase imaging using CT or MRI in subjects with cirrhosis according to AASLD or EASL HCC guidelines is acceptable for study eligibility. Diagnostic imaging hallmarks of HCC include arterial phase enhancement, tumor size, washout, enhancing capsule, and threshold growth. If the subject does not have cirrhosis or these imaging criteria cannot be assessed or are not met, histological or cytological diagnosis of HCC is required for study participation. Ultrasound, angiography, fluorodeoxyglucose (FDG)-positron emission tomography (PET), or AFP cannot be used for clinical diagnosis of HCC. Accreditation for HCC diagnostic imaging, as described in the amended study imaging manual, is required before a site can enroll subjects diagnosed with HCC via imaging alone. Diagnostic scans may be used for screening if they meet the criteria described

in [Section 5.8.6.2](#). For detailed guidance regarding diagnosis of HCC by imaging refer to the amended study imaging manual.

Chest / Abdomen / Pelvis (CAP): CT of CAP or CT chest and MRI abdomen/pelvis will be performed in all subjects at screening (prior to randomization). Tumor assessments after randomization should be performed every 6 weeks (\pm 7 days) through Week 49. After Week 49, these assessments will be performed every 12 weeks (\pm 7 days). CT/MRI of the CAP should include a noncontrast study of at least the liver followed by contrast with triphasic CT imaging of the liver or liver MRI with gadolinium enhanced imaging including triphasic liver.

Other Sites: All other known or suspected sites of disease, including in the brain or bone, are to be imaged by CT/MRI at screening (prior to randomization). Any lesions identified, including bone lesions with a soft tissue component, are to be followed at subsequent tumor assessments as described for CAP above using the same modality as at screening. New suspected lesion sites identified after randomization, including suspected sites of bone or brain lesions, should be assessed by CT/MRI. MRI is the preferred method for brain lesion assessment. If CT of the brain is performed instead of MRI, ambiguous results must be confirmed by MRI. (Note: in order to meet the eligibility requirements of the study, brain metastasis must have been treated and stable for at least 8 weeks before randomization. Subjects without documented brain metastasis during the screening assessment are not required to undergo post-randomization brain imaging unless clinically indicated.)

Tumor assessments should continue on the protocol-defined schedule regardless of whether study treatment is given, reduced, held, or discontinued until a protocol-defined criterion for ending radiographic assessments is met (see [Section 5.8.6.2](#)). Treatment may continue after radiographic progression per RECIST 1.1 as long as the Investigator believes that the subject is still receiving clinical benefit from study treatment and that the potential benefit of continuing study treatment outweighs potential risks (see [Section 5.8.6.3](#)). The same imaging modalities used at screening are to be used for subsequent tumor assessments after randomization.

Radiographic response and disease progression will be determined using RECIST 1.1. Investigators are encouraged, if any doubt or ambiguities exist about radiographic progression, to continue study treatment if the subject is tolerating it acceptably, repeat radiographic tumor imaging at the next scheduled time point, and delay determination of progression until the findings indicating radiographic progression are unequivocal.

Radiographic tumor assessments are to continue until the later of Investigator-determined radiographic progression per RECIST 1.1 or study treatment is permanently discontinued.

For the purpose of determining radiographic study endpoints, central review of radiographic images will be conducted by a BIRC. All radiographic tumor assessments will be sent to the BIRC, which also will review prior radiation history data and prior local therapy information for the purpose of selection of target lesions.

TUMOR MARKER ASSESSMENTS

Tumor marker samples (AFP) will be collected at screening, predose on W1D1, and after first dose of study treatment as described in the schedule of assessments ([Appendix A](#)). The tumor marker assessments will not be used to determine PD in this study. The samples will be analyzed by a central laboratory.

PHARMACOKINETIC ASSESSMENTS

Blood samples will be obtained from all subjects in the experimental arm and the single-agent cabozantinib arms for cabozantinib PK. Samples will be collected for plasma cabozantinib concentration measurement predose on Week 1 Day 1 (W1D1), W4D1, W7D1, W10D1, and W13D1. The results will be used to confirm exposure to cabozantinib and to further characterize the population PK and exposure-response relationships for cabozantinib in this population.

Blood samples will be obtained from all subjects in the experimental arm for atezolizumab PK. Samples will be collected for serum atezolizumab concentration measurement predose on W1D1, W4D1, W7D1, W10D1, W13D1 and FU visits. The results may be used to confirm exposure to atezolizumab.

Collection of PK samples may be halted early or sampling frequency may be reduced at the discretion of the Sponsor.

IMMUNOGENICITY ASSESSMENTS

Blood samples will be obtained from all subjects in the experimental arm (cabozantinib + atezolizumab) for immunogenicity assessment predose on W1D1, W13D1, W25D1, and at the Post-Treatment Follow-up visits (ie, FU-1 and FU-2). Collection of immunogenicity samples may be halted early or sampling frequency may be reduced at the discretion of the Sponsor.

BIOMARKER ASSESSMENTS

Peripheral blood samples will be obtained as specified in the [Appendix A](#). Archival tumor tissue (most recently obtained) will be provided, if available. If archival tissue and histological/cytological confirmation of disease are not available, a tumor biopsy may be collected during screening with subject consent. An optional tumor biopsy may be collected approximately 6 weeks after the first dose of study treatment; other time points may be acceptable provided the tumor sample is collected prior to progressive disease. Exploratory analyses may include, but may not be limited to, the following:

- PD-L1 and MET and other relevant biomarkers in tumor specimens for association with clinical outcomes
- Immune cell infiltration and mutational load assessment in tumor specimens for association with clinical outcome
- Circulating immune cells in peripheral blood
- Blood biomarkers (ie, cytokines/chemokines, VEGF)
- Cell and/or plasma pharmacogenomics (eg, circulating tumor DNA [ctDNA])

Some biomarker samples may only be collected at selected sites (see the study laboratory manual for details). Collection of biomarker samples may be halted early or sampling frequency may be reduced at the discretion of the Sponsor.

HEALTH-RELATED QUALITY OF LIFE

Health-related quality of life assessments will be performed using the EuroQol Health questionnaire instrument EQ-5D-5L. Subjects will be requested to complete the assessment at

baseline (within 14 days prior to randomization) and every 6 weeks thereafter. Subjects will continue completing questionnaires regardless of whether study treatment is given, reduced, held, or discontinued until the date of the last tumor imaging assessment or the study meets its primary endpoints. Consequently these assessments may be required in the Post Treatment Period for some subjects. Subjects should complete the questionnaire on the day of the visit prior to seeing study site personnel. HRQOL assessments will no longer be collected for subjects who transition to the Crossover Phase or if the study transitions to the Maintenance Phase.

HEALTHCARE RESOURCE UTILIZATION

Healthcare resource utilization parameters will be collected from randomization through the 100-Day Post-Treatment Follow-up Visit (FU-2). These include hospital admissions, emergency room visits, intensive care unit admissions, length of stay, surgeries, and transfusions. These data will not be collected in the Maintenance Phase.

STATISTICAL METHODS

The primary efficacy analyses in this study are the comparisons between the combination treatment and control arms for OS and PFS. These analyses will be performed for subjects enrolled in the global enrollment phase which will not include subjects enrolled in the Mainland China Extension Phase. Treatment with cabozantinib in combination with atezolizumab will be inferred to be superior to treatment with sorafenib if the null hypothesis of no difference between arms is rejected in favor of the experimental arm for either OS or PFS. Inflation of Type 1 error associated with multiple primary endpoints and the secondary efficacy endpoint of PFS between single-agent cabozantinib and sorafenib will be controlled by a closed testing procedure that employs a modified Bonferroni procedure, a gatekeeping technique, and the fallback method (see [Section 9.5](#)). The study-wise 2-sided alpha of 5% will be nominally divided between primary endpoints PFS (1%) and OS (4%), with the secondary PFS endpoint tested at the 1% level only if the primary PFS test is successful. If the null hypotheses are rejected for both the primary and secondary PFS endpoints, the 1% alpha for PFS will be reallocated to OS, allowing it to be tested at the 5% level.

Duration of OS is defined as time from randomization to death due to any cause. Duration of PFS is defined as time from randomization to the earlier of either PD per RECIST 1.1 as determined by the BIRC or death from any cause.

The primary analyses of OS and PFS will be event-driven and will be conducted independently after at least the number of events required for each analysis has been observed.

PFS and OS will be summarized descriptively using the Kaplan-Meier method. Inferential comparisons between treatment arms will use the stratified log-rank test. The HR will be estimated using a stratified Cox proportional hazards model. Stratification will be based on the stratification factors used for the randomization as recorded in the Interactive Response Technology (IRT) system.

The study is designed to provide adequate power for analyses of both primary endpoints of PFS and OS comparing the experimental arm with the control arm, and for the analysis of the secondary endpoint of PFS comparing the single-agent cabozantinib arm with the control arm. For the primary endpoints, a larger sample size is needed to provide reasonable power for OS

than is required to evaluate PFS. As a result, if PFS were to be evaluated in the entire study sample required for OS, the PFS events may be biased toward shorter progression times. Thus, to allow longer, more robust PFS follow up among a smaller number of subjects this study employs a “trial within a trial design” (Hessel et al 2016).

The total sample size was planned to be 740 subjects randomized in a 2:1:1 fashion: 370 to the experimental combination arm (cabozantinib + atezolizumab), 185 to the control arm (sorafenib), and 185 to the single-agent cabozantinib arm. However, enrollment commenced under a randomization ratio of 6:3:1 per the original protocol design, and there was a dynamic transition in randomization allocation over time. As a result, the needed enrollment of 185 subjects in the single-agent cabozantinib arm was not expected to be reached at the planned total global enrollment phase sample size of 740 subjects. Therefore, to ensure complete enrollment in the single-agent cabozantinib arm, the total global enrollment phase was extended to accrue a total of approximately 840 subjects.

For primary PFS, a total of 257 events in the first 372 subjects randomized in a 2:1 ratio in the experimental and control arms (n=248 and 124, respectively; defined as the PFS Intent-to-Treat [PITT] population) provide the study with 90% power for a 2-sided log-rank test with a 1% level of significance to detect a hypothesized true HR of 0.6. Assuming an exponential distribution for PFS, this corresponds with a 67% increase in median PFS from 3.6 months to 6.0 months. The minimum observed effect that would result in statistical significance for PFS is an HR of 0.71, a 41% improvement in median from 3.6 to 5.1 months. Interim analysis of the primary PFS endpoint is not planned.

For OS, a total of 368 deaths among all 555 subjects randomized in a 2:1 ratio in the experimental (n=370) and control arms (n=185) are required to provide 90% power to detect an HR of 0.69 using the log-rank test and a 2-sided significance level of 4%. Assuming an exponential distribution for OS, this corresponds to a 45% increase in median survival from 12.3 months to 17.8 months. The minimum observed effect that would result in statistical significance for the primary analysis of OS is an HR of 0.7942, a 26% improvement in median from 12.3 to 15.5 months.

Two interim analyses of OS are planned and will include all subjects in the ITT population available at the time of each analysis. These are planned at the 33% and 66% information fractions. The first interim analysis (IA1) will coincide with the primary analysis of PFS and will be performed only if the null hypothesis for primary PFS is rejected and is expected to occur at approximately the 33% information fraction. Should the timing of IA1 trend towards an information fraction much higher than expected (eg, due to faster-than-expected deaths or slower-than-expected PFS events), the plan for the interim analyses of OS may be modified (see [Section 9.8](#)). Inflation of Type 1 error associated with these interim analyses will be controlled using Lan-DeMets O’Brien-Fleming (LD-OF) alpha-spending functions based upon a 4% total alpha allocation for OS.

The secondary analysis of PFS for the single-agent cabozantinib arm vs the control (sorafenib arm) will be performed for subjects enrolled in the global enrollment phase which will not include subjects enrolled in the Mainland China Extension Phase. For this analysis, a total of 283 events among all 370 subjects (185 per arm) in the single-agent cabozantinib and control arms provides the study with 85% power for a 2-sided log-rank test with a 1% level of significance to detect a hypothesized true HR of 0.65. Assuming an exponential distribution for PFS, this

corresponds with a 53% increase in median PFS from 3.6 months to 5.5 months. The minimum observed effect that would result in statistical significance for PFS is an HR of 0.735, a 36% improvement in median from 3.6 to 4.9 months.

An interim analysis of secondary PFS is planned contemporaneously with the primary PFS analysis and will include all subjects in single-agent cabozantinib and control arms of the ITT population available at the time of the analysis. This is anticipated to be at 67% information fraction (to be performed only if the null hypothesis for PFS is rejected). Inflation of Type 1 error associated with these interim analyses will be controlled using Lan-DeMets O'Brien-Fleming (LD-OF) alpha-spending functions based upon a 1% total alpha allocation for secondary PFS.

With a constant accrual rate of 30 subjects per month, it is anticipated that it will take approximately 18.4 months to observe the required primary PFS events (16.5 months of subject accrual) and approximately 38 months to observe the required deaths for OS (25 months of subject accrual) to evaluate the primary endpoints in the combination and control arms. Assuming the same accrual rate, it is anticipated that it will take approximately 25 months to observe the required secondary PFS events (25 months of subject accrual) to evaluate the secondary endpoint in the single-agent cabozantinib and control arms. The true intervals required to meet these milestones may be longer or shorter due to divergence from assumptions, including non-constant accrual rate due to the time required for all study sites to become active, or due to the impact of the global COVID-19 pandemic on subject enrollment and other aspects of study conduct.

The sample size for the global study may be increased up to an additional 25% if a review of the accumulating data suggests that the COVID-19 pandemic has caused the rate of study dropout or non-compliance to increase to a degree that the ability to adequately evaluate study endpoints may be undermined. The Mainland China Extension Phase will not be expanded beyond 148 subjects.

China Subpopulation: The primary scope of the China subpopulation analysis is to allow evaluation of consistency in efficacy and safety with the global study population per NMPA guidance. Since the China subpopulation is not powered to demonstrate statistical significance in terms of efficacy, no formal hypothesis testing will be performed. All data summaries for the China subpopulation will be descriptive. The safety and efficacy data in the China subpopulation will be analyzed separately for the same endpoints using the same analysis methods as for the global population. The analyses for this subpopulation will be performed when the data are of sufficient maturity to allow evaluation of consistency in efficacy and safety.

TABLE OF CONTENTS

PROTOCOL SYNOPSIS	4
TABLE OF CONTENTS.....	25
LIST OF ABBREVIATIONS.....	32
1. BACKGROUND	36
1.1. Hepatocellular Carcinoma	36
1.2. Cabozantinib	37
1.3. Atezolizumab	39
1.4. Combination of Cabozantinib and Atezolizumab.....	42
1.5. Rationale	43
1.5.1. Rationale for Evaluating Cabozantinib in Combination with Atezolizumab in Advanced HCC	43
1.5.2. Rationale for Study Design.....	44

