3 ANALYSIS POPULATIONS

The planned analysis populations are briefly summarized in Table 4. The populations specified below pertain to the global study population and do not include the subjects enrolled in the China Extension Phase. The addendum to Protocol amendment 2 allowed for the global enrollment (excluding the China Extension Phase) to be up to 840 subjects to ensure enrollment of at least 185 subjects in the single agent cabozantinib arm. The study enrolled 188 subjects in the single agent cabozantinib arm in the global study population. The 188th subject randomized to the single agent cabozantinib arm was considered the last subject in the global study population of 837 subjects. Subjects randomized in China after this date are in the China Extension Phase only. Analyses that include the China Extension Phase are beyond the scope of this plan. Further information on the global study population is provided in the sections below.

Table 4: Analysis Populations for the Global Study Population

Analysis	Population	Subjects
Primary PFS	PITT	First 372 subjects randomized to experimental or control arms
Primary OS	ITT	All subjects randomized to experimental or control arms
Secondary PFS	ITT	All subjects randomized in control and single-agent cabozantinib arms
Additional efficacy analyses	ITT	All randomized subjects in the three treatment arms
Safety analyses	Safety	All subjects who received any study treatment
Safety analyses for PITT subjects	P-Safety	All subjects who received any study treatment in the PITT population

All populations exclude the China Extension Phase.

ITT, Intent-to-Treat; OS, overall survival; PFS, progression-free survival; PITT, PFS Intent-to-Treat; P-Safety, PFS Safety

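### The stated analysis sizes (555 for OS, 370 for secondary PFS) and the timings beside them belong to the superseded 740-subject plan and were not updated when global enrolment was extended to about 840

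*Protocol*

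**What the plan says.** Protocol synopsis (Statistical Methods) and section 9.7 describe 740 subjects as the plan, then report that "the total global enrollment phase was extended to accrue a total of approximately 840 subjects", so that the single-agent arm would reach 185. The paragraphs that follow still size the analyses on the old total.

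- OS: "For OS, a total of 368 deaths among all 555 subjects randomized in a 2:1 ratio". On the median scale, "this corresponds to a 45% increase in median survival from 12.3 months to 17.8 months".
- Secondary PFS: "a total of 283 events among all 370 subjects (185 per arm) in the single-agent cabozantinib and control arms".
- Timing at 30 subjects per month: 25 months of accrual, about 38 months to the required deaths and about 25 months to the required secondary PFS events. The secondary PFS interim is anticipated at 67% information.

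Protocol Table 33 and SAP Table 3 repeat these values. Protocol section 3.2 still gives 25 months to randomize 740.

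The SAP, dated 05 February 2021, states in section 3 that "The study enrolled 188 subjects in the single agent cabozantinib arm in the global study population", and that this population has 837 subjects. Its Table 4 assigns OS to all subjects randomized to the experimental or control arm, and secondary PFS to all randomized to the control or single-agent arm. SAP 2.1 pairs a total of about 840 with arms of about 370, 185 and 185, which add up to 740.

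**The concern.** Only the primary PFS population is capped by order of randomization (the first 372, extendable to 410). The OS and secondary PFS sets have no cap, so every subject added by the extension enters at least one of them. The statements that OS covers all 555 subjects and secondary PFS all 370 therefore contradict the definitions of the analysis sets.

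The timings have the same origin. With more subjects at risk and a fixed death target, the final OS analysis comes earlier after first randomization, with shorter minimum follow-up and a smaller proportion of deaths. Anyone using the text to plan the read-out, or to judge how mature the OS result will be, gets figures for a trial that was not run.

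**Working it through.** **Inputs.** OS: 368 deaths, HR 0.69, two-sided alpha 4%, power 90%, 2:1, medians 12.3 and 17.8 months. Secondary PFS: 283 events, HR 0.65, two-sided alpha 1%, power 85%, 1:1, medians 3.6 and 5.5 months. Accrual is 30 per month and event times are exponential (protocol synopsis and 9.7). Total 837, single-agent 188 (SAP 3). No dropout rate is stated.

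**1. Event targets.** Schoenfeld: d = (z₁₋α/₂ + z_power)² / [p(1−p)(ln HR)²].
- OS: (2.054 + 1.282)² / [(2/9)(0.3711)²] = 364, against 368 stated. Power at 368 is 90.4%.
- Secondary PFS: (2.576 + 1.036)² / [(1/4)(0.4308)²] = 282, against 283 stated. Power at 283 is 85.3%.

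**2. The plan's timings for 740 subjects.** For accrual at rate r from time a to b, and hazard λ = ln 2/median, the expected events by time t are r[(b−a) − (e^(−λ(t−b)) − e^(−λ(t−a)))/λ]. Accrual ends at 740/30 = 24.7 months.
- OS at 38.2 months: 229.6 experimental (15 per month) + 138.4 control (7.5 per month) = 368. Stated: 38.
- Secondary PFS at 25.3 months: 132.3 + 150.7 = 283. Stated: 25.
- The same method puts the 257th primary PFS event at 18.4 months, as stated.

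The printed timings are therefore the 740-subject, 2:1:1, zero-dropout figures.

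**3. N after the extension.** OS set: 837 − 188 = 649, with no assumption needed. The experimental-to-control ratio is 2:1 under both 6:3:1 and 2:1:1, so the split is about 433 vs 216. Secondary PFS set: 188 + 216 = about 404.

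**4. Timings for 837 subjects.** Enrolment takes 837/30 = 27.9 months. The protocol describes the ratio change as dynamic without giving dates, so I assume one switch. If x subjects entered under 6:3:1, then 0.10x + 0.25(837 − x) = 188, which gives x ≈ 142, or the first 4.7 months.

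| At 30/month, no dropout | 740 plan | 837 subjects |
|---|---|---|
| End of enrolment (months) | 24.7 | 27.9 |
| 368th death (months) | 38.2 | 34.0 |
| Minimum OS follow-up (months) | 38.2 − 24.7 = 13.5 | 34.0 − 27.9 = 6.1 |
| Deaths / OS set | 368/555 = 66% | 368/649 = 57% |
| 283rd secondary PFS event (months) | 25.3 | 26.1 |
| Events / secondary PFS set | 283/370 = 76% | 283/404 = 70% |

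The switch assumption matters little: spreading each arm evenly over 27.9 months gives 34.4 months for OS and 25.8 for secondary PFS.

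**5. Sensitivity.** A dropout hazard of 0.01 per month puts the 368th death at 37.4 months for 837 subjects, against 44.9 for 740. Dropout delays both, but the extended trial still reaches the target earlier. For secondary PFS at 837 subjects, a censoring hazard of 0.01, 0.02 or 0.03 per month gives 27.0, 27.9 or 28.9 months.

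**6. Power after the extension.** OS stays at 2:1, so 90.4% is unchanged. Secondary PFS at 188:216 has p(1−p) = 0.2488, and power at 283 events is 85.1%.

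**The case against.** The best defence is that nothing inferential is wrong. Both analyses are event-driven, the SAP says they will run at the protocol's event counts, and power rests on those counts. The extension itself is disclosed, the protocol gives the experimental and control arms as at least 370 and 185, SAP Table 3 labels its arm sizes as planned, and both documents say that intervals may differ. The power point stands in full. The disclosure points stand only in part: the label covers the arm-size row and not the N-for-analysis row, and the caveat covers departures from assumptions, not figures computed for a replaced total.

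A reader might also infer more than the documents support.

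- *The design is undersized, or 368 and 283 need to change.* They do not (steps 1 and 6).
- *A stated OS maturity is wrong.* No percentage is stated; 66% is only implied by 368/555.
- *The secondary PFS cut will precede full single-agent enrolment.* At 30 per month with no censoring it would (26.1 vs 27.9 months, about 175 of 188 randomized). The two coincide at a censoring hazard of about 0.02 per month, and the order reverses at 40 per month (21.0 vs 20.9). The 740 plan already put the trigger near the end of accrual. The SAP reports all 188 enrolled and describes the 283-event analysis as still to come, so no live risk is shown.
- *The secondary interim will be at 57%, not 67%.* The 57% needs zero censoring, 30 per month and the assumed switch. With 0.02–0.04 per month censoring and 30–40 per month accrual the range is 60–78%, which includes 67%. Critical values follow the actual fraction in any case.
- *The China target is no longer 20%.* Protocol 9.7 computes that percentage on N = 740 explicitly, and 148/740 = 20%.

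**Conclusion.** The point holds as a documentation error in both governing documents. The analysis sizes of 555 and 370 are wrong as written: the OS set is 649 by subtraction, and the secondary PFS set is about 404, taking control as one third of 649. The accrual and OS timings are correct only for 740 subjects. On the plan's own assumptions, enrolment lengthens from 25 to about 28 months and final OS moves from about 38 to about 34 months, with deaths in about 57% of subjects. Secondary PFS timing moves by only about one month.

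The timings rest on constant accrual of 30 per month, exponential event times, no dropout and a single switch of ratio; the 649 rests on none of these. The actual accrual rate is not given. Event targets, power and the China cap are unaffected.

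**What to change.** In the protocol synopsis, section 9.7/Table 33 and SAP 2.3/Table 3:

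1. Restate N for analysis as 649 for OS (about 433 vs 216) and about 404 for secondary PFS (188 vs about 216), using the exact arm counts once confirmed. Keep 555 and 370 only if they are labelled as the superseded plan.
2. Restate expected timing at 30 per month with no dropout: enrolment about 28 months; 368 deaths at about 34 months, in about 57% of subjects; 283 secondary PFS events at about 26 months, or about 28 with 0.02 per month censoring.
3. Re-derive the anticipated 67% secondary interim fraction and state the accrual and censoring assumptions behind it.
4. Bring protocol 3.2 and the arm sizes in SAP 2.1 into line with the extended total.

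Leave 368, 283, the stated power and the cap of 148 as they are. No new secondary PFS cut-off rule is required. A minimum follow-up condition would delay that read-out, could leave the second OS interim at 4% alpha, and would change a cut-off rule after SAP sign-off in an open-label trial. The cost is wording only; the expected OS maturity simply reads as less favourable than the present text implies.
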